#### 2.2.2 Secondary objectives

The TirolGESUND study is novel type of participatory, lifestyle intervention study and may represent a considerable effort for participants. Few studies have so far so comprehensively evaluated health parameters longitudinally. Therefore, we will describe and report general study characteristics relating to participation and dropout, and evaluate changes, as well as dynamics, in several biological markers, including molecular (epigenetic, genetic, microbial, metabolic), clinical, and psychological (see 5.4.2).

We are also interested in investigating the spatial and temporal dynamics of DNA methylation changes in response to lifestyle intervention and will hence be investigating changes over time in different surrogate samples (cervical, buccal, blood) using mixed-effects models, and moreover investigate whether surrogate tissue DNA methylation changes occur in a synchronous or discordant manner.

Lastly, we will explore dynamics of other biomarkers and indicators of health and disease, including microbiome, metabolome, inflammation, body composition and smoking status, vascular health, pulmonary health, physical activity, and health-related quality of life.

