#### 6.4.4 Secondary endpoint reporting

To investigate the magnitude and temporal dynamics of changes in methylation indices for each surrogate tissue, namely cervical, buccal, and blood, linear mixed-effects models will be estimated, combining tissues where applicable. The use of random slopes and intercepts will be explored (R package lme4 or nlme, lmer function). Compliance score, sample cell composition, BMI, smoking status, or other factors identified during exploratory data analysis may be used as covariates. Additionally, in a descriptive manner, the change from baseline will be reported within each tissue and paired comparisons will be carried out. Examples of linear models (covariates may be altered or extended) are provided below:

$$model_{intermittent \ fasting} = lmer(score \sim compliance + sample \ type + BMI + ic + age_{baseline} + (time|id), data = data)$$
(1)

$$model_{smoking \ cessation} = glmer(score \sim compliance + sample \ type + smoking \ status + ic + age_{baseline} + (time|id), data = data)$$
(2)

Separate models per sample type may be even more informative, this will be explored during exploratory data analysis.

Using models based on equations in equations 1 and 2, the data will be characterised as follows:

- 1. Estimation of average changes in all participants
- 2. Estimation of changes for individual participants
- 3. Characterisation of degree of heterogeneity across participants (variance across participants, quantified by random effects)
- 4. Identify factors (fixed effects) that predict changes (e.g. compliance score)

Beta estimation will be conducted using maximum likelihood estimation. Following model fitting, residuals will be visualised and qq plots will be generated. If p values are needed for reporting, these will be obtained via Kenward-Roger estimation in the R package lmerTest. A sensitivity analysis will be conducted using either complete case analysis or multiple imputed values

Comparison between sample types may be done via incorporation of data into mixed effects models with an additional covariate (sample type). The sample type with the biggest changes in association with the compliance score may be the most suitable surrogate type for monitoring longitudinal health effects.

Data will be visualised using spaghetti plots, colouring by compliance score and applying facet wraps by sample type.

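### Equations (1) and (2) in SAP section 6.4.4 carry time only as a random slope, so they have no parameter for average change, predictors of change or tissue differences in change

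*SAP*

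**What the plan says.** Section 6.4.4 states the purpose of the mixed models: "To investigate the magnitude and temporal dynamics of changes in methylation indices for each surrogate tissue". It introduces the two formulas with "Examples of linear models (covariates may be altered or extended) are provided below".

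- Equation (1), intermittent fasting, has fixed terms for compliance, sample type, BMI, immune cell composition and baseline age: "type + BMI + ic + age_{baseline} + (time|id), data = data".
- Equation (2), smoking cessation, has smoking status in place of BMI: "status + ic + age_{baseline} + (time|id), data = data".

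Four outputs are then to come from models built on these equations. Output 1 is "Estimation of average changes in all participants". Output 2 is change in individual participants, and output 3 is heterogeneity between participants, read from the random effects. Output 4 is "Identify factors (fixed effects) that predict changes (e.g. compliance score".

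On tissues the section says "Comparison between sample types may be done via incorporation of data into mixed effects models with an additional covariate (sample type". The corresponding aim in section 2.2.2 is to "investigate whether surrogate tissue DNA methylation changes occur in a synchronous or discordant manner". Section 7 repeats that aim and asks about agreement in both direction and timing.

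**The concern.** Every output in the list concerns change over time, yet neither formula has a fixed effect of time or an interaction with time. An analyst who runs the equations as printed gets a model in which the average woman does not change. The size of the average effect would be missing. The spread of individual responses would look larger than it is. A non-significant compliance coefficient could be taken to mean that adherence does not matter, or a significant one to mean that it does, when the coefficient does not measure that. Section 6.4.4 also suggests that the tissue whose changes relate most strongly to compliance may be the best surrogate for monitoring. The equations have no term for that comparison.

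**Working it through.** **The plan's own figure.** The one design calculation is in section 3.6: n = 60, difference 0.2, SD 0.44, α = 0.05. A two-sided paired z test gives Φ(0.2/(0.44/√60) − 1.96) = Φ(3.52 − 1.96) = Φ(1.56) = 0.94, as stated. This fixes neither a slope SD nor a residual SD. The structural steps below need no such figure; the numerical ones rest on assumed variances.

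**Step 1: average change.** In lme4 syntax, (time|id) gives each woman a random intercept and a random slope, both deviations with mean zero around the fixed part. With no time in the fixed part, the mean slope is constrained to 0. Coding time as a visit factor, an option in section 5.2, does not help: the random visit effects are then also centred on zero.

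**Step 2: heterogeneity.** If true slopes have mean m and SD s, a slope distribution forced to have mean 0 has apparent SD of about √(s² + m²). With m = −0.2 over six months:

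| Assumed s | Formula | Ratio to truth | Simulated |
|---|---|---|---|
| 0.20 | √(0.04 + 0.04) = 0.283 | 1.41 | 0.287 |
| 0.10 | √(0.01 + 0.04) = 0.224 | 2.24 | 0.22 |

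The first row comes from 100 simulated trials of the pooled form: 60 women, four visits, three tissues sharing one slope, intercept SD 0.4, residual SD 0.25. The second comes from 80 simulated trials without tissues: 60 women, four visits, intercept SD 0.4, residual SD 0.2. In the first setting the predicted slopes averaged −0.14 against a true −0.20. With fixed time added, the mean change was estimated at −0.207 and the slope SD at 0.197.

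**Step 3: predictors of change.** Section 3.4 builds the compliance score from the days between visits and gives no baseline value. Two codings are possible.

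- *Constant per woman.* Compliance was made to predict change truly (−0.5 per unit). Its main effect was significant in 7% of 100 runs; a time × compliance term was significant in 55% (simulation standard error √(0.55 × 0.45/100) = 5 points). When compliance was unrelated to change, the rates were 5% and 9%. The main effect therefore has almost no power for output 4.
- *Varying, with 0 at baseline.* Compliance then separates baseline from later visits and stands in for time. When it was unrelated to change, it was still significant in 84% of runs in the first setting and 96% in the second.

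**Step 4: tissues.** Sample type is a main effect, so it shifts level. Each woman has one random slope shared by cervix, buccal and blood. No time × sample type term exists, so discordant change cannot be expressed. This step is structural; no discordant-tissue simulation result is available.

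**Step 5: covariates affected by the intervention.** Sections 3.1 and 4.1.1 admit to the smoking sub-study only women smoking at least 10 cigarettes a day for five years. Smoking status at entry is therefore the same for all of them, and the term in equation (2) can vary only after baseline. It adjusts for quitting, the direct result of the intervention. In equation (1) only age carries a baseline subscript, so the timing of BMI is unclear.

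**The case against.** The strongest reply is that the formulas are labelled examples, belong to secondary analyses in a study that calls itself exploratory, and may be changed. That lowers the weight of the point but does not remove it. The permission concerns covariates, the four outputs are tied to these equations, and no other section puts time in the fixed part. Section 5.2 discusses only how timing is coded.

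A second reply is that much of the information comes by other routes. Section 6.4.4 also plans change from baseline and paired comparisons within each tissue. Section 6.4.2 plots individual slopes against covariates and tabulates results by median compliance. Separate tissue models are allowed. This stands in part. The paired comparisons do give within-tissue change, but not a modelled time course or a test of predictors of change, and a separate tissue model of the same form still lacks fixed time.

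A reader might infer three stronger things that the SAP does not support.

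- *That average change cannot be estimated at all, or that the primary result is compromised.* Section 6.4.3 names paired Wilcoxon tests at baseline and month 6, which do not use these equations. Section 5.4.1 allows a mixed model for the primary intention-to-treat analysis but prints no formula for it.
- *That compliance will be falsely significant in most trials, or that the slope SD will double.* The 84% and 96% need a baseline coding of 0, which the SAP does not state, and the inflation depends on an assumed slope SD.
- *That equation (1) adjusts for weight loss.* This would rest on a missing subscript alone.

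**Conclusion.** The point holds for both equations as printed. They constrain the mean slope to zero, leave output 1 without a parameter, overstate output 3, and give level effects where output 4 and the tissue comparison need effects on change. The inflation of the slope SD is about 1.4-fold if the slope SD equals the mean change and about 2.2-fold if it is half of it. What happens to the compliance coefficient depends on coding: it is a proxy for time if compliance is 0 at baseline, and a test with little power for change if compliance is constant per woman. Adjustment for quitting in equation (2) follows from the SAP's own eligibility rule; for BMI in equation (1) there is only an ambiguity to resolve. The primary paired Wilcoxon analysis and the within-tissue paired comparisons stand. The equations should be corrected before the secondary analyses are run.

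**What to change.** 1. Put time in the fixed part of both equations, as a visit factor or as days since baseline (section 5.2 allows either). Read average change from these terms.
2. In pooled models add time × sample type, random intercepts for tissue within woman and, where estimable, tissue-specific random slopes. Without those slopes each woman still has one slope for all tissues, and only discordance of tissue means can be tested. With four visits per woman and tissue, the random slopes should use continuous time even if the fixed part uses visit. The alternative is separate tissue models that include fixed time.
3. Assess adherence in a separate model with time × compliance, and with time × compliance × sample type where the surrogate tissue is chosen. State whether compliance is per woman or per interval, and its value at baseline.
4. In equation (1), specify baseline BMI. In equation (2), leave post-baseline smoking status out of the model that estimates average change.
5. If the mixed model allowed in section 5.4.1 is used, give it the same fixed time term.

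Two pieces of tidying fit the same edit but do not bear on the conclusion. Equation (2) calls glmer for continuous scores, and maximum likelihood is named beside Kenward-Roger inference, which is built on REML.

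The cost is SAP wording and two lines of code, with no new data. The downside is a few more parameters, and the tissue-specific slopes may not all be estimable with 60 women per group.

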#### 6.4.2 Exploratory analysis

Initial data exploration will assess the association of cancer risk- and age-associated signature scores with immune cell composition. DNAme signature scores of interest highlighted above (e.g. but not limited to WID-BC, WID-OC, WID-EC, WID-CIN, WID-REA, WID-SOLA) at month 0 will be visualised as follows:

- chronological age
- immune cell composition (ic)
- BMI
- smoking status

for each tissue, amongst other molecular and cellular analyses. It is assumed that epigenetic indices should be corrected for immune cell composition (for blood: myeloid fraction, consisting of monocyte, eosinophil and neutrophil composition) using baseline values for all participants in a given study arm.

To investigate longitudinal effects, spaghetti plots will be generated for all timepoints (baseline, M2, M4, M6; adjusted for age (across groups) and immune cell composition (ic)), grouping or colouring by the following variables:

- compliance score (colour gradient), separate for each intervention (smoking cessation, intermittent fasting with ketogenic supplement, intermittent fasting without ketogenic supplement)
- smoking status at the end of the intervention (smoking cessation only)
- delta BMI month 6 and month 0 (colour gradient) (intermittent fasting only)
- average  $\beta$ -hydroxy butyrate value (colour gradient) (subgroup of intermittent fasting only)

The suitability of random intercepts and slopes will also be explored during exploratory analysis. Individual slopes for scores will be plotted against covariates.

In addition to visualisation, summary tables (median and standard deviation) will be generated per group per timepoint, assessing cross-sectional (between groups) and longitudinal differences (within subjects), stratifying median compliance score.

To evaluate potential associations between changes in epigenetic scores and clinical or other factors, visualisation plots may be generated and covariate adjustment may be conducted for primary and secondary analyses, where appropriate.

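### The example pooled-tissue models give cell composition one common slope, although the covariate is the myeloid fraction in blood and immune cell composition otherwise

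*SAP*

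**What the plan says.** SAP section 6.4.2 abbreviates the composition covariate as "immune cell composition (ic") and names a specific variable for one tissue only: "for blood: myeloid fraction, consisting of monocyte, eosinophil and neutrophil composition". It gives no separate definition for cervix or buccal.

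Section 6.4.4 states that "linear mixed-effects models will be estimated, combining tissues where applicable". Equation 1 (intermittent fasting) ends "BMI + ic + age_{baseline} + (time|id), data = data" and equation 2 (smoking cessation) ends "ic + age_{baseline} + (time|id), data = data". In both, sample type and ic are separate additive terms with no product between them.

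The equations are introduced with the words "Examples of linear models (covariates may be altered or extended) are provided below". The section adds: "Separate models per sample type may be even more informative, this will be explored during exploratory data analysis". On comparing tissues it says "Comparison between sample types may be done via incorporation of data into mixed effects models with an additional covariate (sample type"), and it suggests that the tissue whose changes are largest in relation to compliance may be the best surrogate. The summary table in section 6.16 lists the three tissues both separately and combined, so a pooled analysis remains in the plan.

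**The concern.** A sample type main effect moves only the intercept for each tissue. It does nothing for the slope on ic. A given value of the myeloid fraction in blood does not mean the same as that value of immune cell composition in a cervical or buccal sample, and the SAP gives no reason to expect the two to relate to a score with the same slope. A single coefficient is then roughly an average of the tissue slopes, weighted by how widely ic varies in each tissue, and can be wrong for all of them.

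The SAP regards this adjustment as important: section 6 says that cell composition is known to influence methylation. It also leaves room for composition to move, since inflammatory cell markers in blood are secondary endpoints (5.4.2) and fewer inflammatory cells are an anticipated finding in the single-cell subgroup (5.4.3). If composition moves and is removed with the wrong slope, the remainder looks like a methylation change. At stake in section 6.4.4 are the fixed effects used to identify predictors of change, compliance being the named example, and any pooled comparison of tissues.

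**Working it through.** **1. The only design figure.** Section 3.6 gives n = 60, difference 0.2, SD 0.44, power 0.94. Read as a paired comparison: 0.44/√60 = 0.0568; 0.2/0.0568 = 3.52; 3.52 - 1.96 = 1.56; Φ(1.56) = 0.94. It reproduces. The argument does not depend on it; 0.2 serves below only as a yardstick.

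**2. What the printed models can estimate.** Fixed effects in equation 1 are the intercept, compliance, sample type, BMI, ic and baseline age; equation 2 has smoking status in place of BMI. There is no fixed time effect and no sample type × time, sample type × compliance or sample type × ic term. The random time slope belongs to the participant and is shared by her tissues.

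**3. Formula.** Let b_k be the true ic slope in tissue k, s_k the SD of ic, and Δ_k the shift in ic.

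- Common slope: b_c ≈ Σ s_k² b_k / Σ s_k²
- False change in tissue k, once the model has tissue-specific time terms: (b_k - b_c) × Δ_k

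**4. Numbers.** All are assumptions, as the SAP gives none: slopes -1 (cervix, buccal) and +0.5 (blood); SD of ic 0.2, 0.2 and 0.08; myeloid fraction falls by 0.05; no true change.

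- b_c = (-0.04 - 0.04 + 0.0032)/(0.04 + 0.04 + 0.0064) = -0.0768/0.0864 = -0.89
- False blood change = (0.5 + 0.89) × (-0.05) = -0.07, about a third of 0.2

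Simulation (60 women, 3 tissues, 4 visits, 200 runs per row, tissue-specific time terms added):

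| Slopes: cervix and buccal / blood | Common ic slope: blood change | Tissue-specific ic slopes |
|---|---|---|
| -1 / +0.5 | -0.066 | 0.003 |
| -0.5 / +0.25 | -0.034 | 0.001 |
| -1 / 0 | -0.047 | -0.001 |

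**5. Compliance coefficient with the printed fixed effects.** Here Δ is the shift in ic per unit of compliance. With equal numbers of samples per tissue and a shift in blood only, the pooled coefficient takes up about one third of the blood error: -0.07/3 = -0.02 for a shift of 0.05, and twice that, about -0.05 from unrounded values (1.389 × 0.10/3 = 0.046), for 0.10. Simulation with the first slope set gave about -0.02 and -0.05. Tissue-specific ic slopes removed it.

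**6. When the bias is absent.** A second simulation used different assumptions: slopes -1, -1 and +1, rising ic, 150 runs, participant fixed effects, tissue × time added. It estimated the blood-minus-cervix difference in change, with truth 0.

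| Scenario | Common ic slope (rejection) | ic × tissue (rejection) |
|---|---|---|
| No shift in ic | -0.001 (4.7%) | -0.002 (6.0%) |
| Shift 0.05, all tissues | 0.101 (38.7%) | -0.001 (4.7%) |
| Shift 0.05, blood only | 0.060 (16.7%) | -0.004 (5.3%) |
| Shift 0.10, blood only | 0.131 (54.7%) | -0.007 (2.0%) |
| Equal slopes, shift 0.05 in blood | 0.006 (4.0%) | 0.006 (4.0%) |

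Where the slopes differed, the fitted common slope was -0.33 to -0.35, which is right for no tissue.

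**The case against.** A reader might infer that the plan as printed creates false tissue differences in change. The documents do not support that. By step 2, equations 1 and 2 hold no parameter for a tissue-specific change, true or false. The simulated blood changes come from a model with added terms, and adding `sample type * ic` alone would not supply them. This part of the objection stands in full.

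The equations are also labelled examples, pooling is limited to where it applies, change from baseline is to be reported within each tissue, and separate models are already contemplated. It would therefore be too strong to say that all tissue conclusions rest on the pooled model. But the permission to alter covariates carries no warning that ic changes meaning between tissues, the choice is deferred to data exploration, and the section says the data will be characterised with models based on these equations.

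The bias is conditional and its inputs are assumed; the largest figures use slopes of opposite sign. The 0.2 in section 3.6 is a sample-size difference, not a threshold for tissue contrasts.

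Finally, section 6.4.2 speaks of correcting the indices using baseline values, and section 6.4.3 tests adjusted scores. Whether the score in equations 1 and 2 is already composition-adjusted is not stated. If it were correctly adjusted in each tissue beforehand, the remaining ic slopes, and hence the bias, would be near zero. That uncertainty stands, although the equations still carry ic as a covariate.

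**Conclusion.** The point holds as a weakness of two example secondary models. A covariate defined differently in blood shares one coefficient with the other tissues, so the adjustment is mis-specified unless the slopes coincide. Harm needs both unequal slopes and a shift in composition with time or compliance. It can then reach the compliance coefficient even with the printed fixed effects (about -0.02 to -0.05 for assumed shifts of 0.05 to 0.10). It can reach tissue differences in change only after tissue × time or tissue × compliance terms are added.

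Under the assumptions in step 4, the false blood change is about -0.05 to -0.07, or about -0.03 with slopes of -0.5 and +0.25. The true size cannot be known from the SAP, and it is zero with stable composition or equal slopes. The primary endpoint, a paired comparison in cervical samples alone, is not touched. The correction is worth making because it is specific and nearly free, not because a main conclusion is in danger.

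**What to change.** - In equations 1 and 2, replace the additive `sample type + ic` by `sample type * ic`, and define ic for each tissue: the myeloid fraction for blood, and the variable intended for cervix and for buccal.
- Keep that product in any pooled model used to compare tissues, together with a fixed time effect and the sample type × time or sample type × compliance term that the comparison requires.
- Alternatively, make the separate per-tissue models already allowed in section 6.4.4 the stated basis for tissue-specific conclusions.
- State whether the score in these equations is raw or already adjusted for composition.

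The ic product costs two extra coefficients per model (three tissues, one reference) and a change of SAP wording. The time and compliance interactions cost more coefficients, but any tissue comparison of change needs them anyway. No new data are needed.

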## 3.6 Sample size

The sample size of n = 60 per group is based on an initial estimation of the potential clinically relevant effect and variance as part of the preceding FORECEE project: a total of 60 participants are required to detect a difference of 0.2 in DNA methylation indices (e.g. WID-BC index), assuming a standard deviation of 0.44, at a statistical power of 0.94 and a significance level of 0.05. There are no preliminary data for longitudinal changes in the WID scores, thereby TirolGESUND acts as a pilot study to define effect sizes and variance for larger prospective studies in the future.

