# 5 Statistical principles

# 5.1 Significance levels and adjustment of p-values for multiplicity

Significance levels throughout are set at p < 0.05. Formal adjustment for primary and secondary outcomes may be conducted using Benjamini-Hochberg or Bonferroni correction as appropriate, although formal adjustments may not be strictly necessary for outcomes of more exploratory or descriptive nature, as previously argued. For subsidiary outcomes, no formal correction will be applied. 95% confidence intervals will be presented for estimates of effects throughout.

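### Section 6.4.4 pairs maximum likelihood estimation with Kenward-Roger p-values, which do not describe one fit, and leaves the method for the 95% intervals open

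*SAP*

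**What the plan says.** Section 6.4.4 sets out mixed models for the methylation scores across time and tissue. On estimation it states "Beta estimation will be conducted using maximum likelihood estimation". On testing it states "If p values are needed for reporting, these will be obtained via Kenward-Roger estimation in the R package lmerTest". REML is not mentioned anywhere in the SAP.

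Equation 1 (diet) is printed as an lmer call with no argument that switches from lmer's REML default to ML. Equation 2 (smoking) is printed as a glmer call with no family, for the same kind of score.

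Among the results to be reported, item 3 of the same section lists the heterogeneity between women, measured by the random effects. Item 4 lists the fixed effects that predict change, with compliance as the example.

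Section 5.1 adds "95% confidence intervals will be presented for estimates of effects throughout" and "Significance levels throughout are set at p < 0.05". Neither section says how a mixed-model interval is to be built.

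**The concern.** Kenward-Roger is a small-sample adjustment of the covariance matrix and degrees of freedom of a REML fit. A plan that estimates by ML and tests by Kenward-Roger therefore uses one fit for the estimates and, in effect, another for the p-values. Two analysts could follow section 6.4.4 faithfully and report different intervals for the same effect.

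Two things are at stake.

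- **Variance components.** ML takes no account of the degrees of freedom spent on fixed effects, so between-woman variances come out too small. This does not depend on how intervals are built. Section 3.6 presents the study as a pilot that should supply effect sizes and variances for later trials, so these variances are a deliverable.
- **Intervals.** If the 95% intervals were taken from the ML fit with a normal quantile, they would be narrower than the Kenward-Roger ones. An interval could exclude zero beside a p-value above 0.05. The compliance effect is the most exposed, and section 6.4.4 uses it to suggest which tissue is the best surrogate.

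**Working it through.** **The plan's own figure.** The SAP gives no figure for interval performance. Its one design figure is in section 3.6: "a total of 60 participants are required to detect a difference of 0.2 in DNA methylation indices", "assuming a standard deviation of 0.44, at a statistical power of 0.94 and a significance level of 0.05". For a paired comparison, power = Φ(0.2/0.44 × √60 − 1.96) = Φ(3.52 − 1.96) = Φ(1.56) = 0.941; the t version gives 0.934. The stated 0.94 is reproduced and is not in dispute. It serves here only to confirm n = 60 as the working size.

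**Sample sizes, all from the SAP.** 120 is the whole diet sub-study (3.1). 60 is the smoking sub-study or one diet arm (3.1). 30 is the per-protocol threshold (5.2, 6 and 6.4.3), and also half of 60 under a median split. The table in 6.16 lists longitudinal mixed models for the per-protocol or median-split sets.

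**Variance bias.** In a balanced design reduced to one mean per woman, with p between-woman parameters, ML estimates the variance of those means with expectation (n − p)/n of its true value.

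- p = 5: 115/120 = 0.958, 55/60 = 0.917, 25/30 = 0.833, so about 4%, 8% and 17% too low.
- p = 2 (intercept and baseline age only): 118/120 = 0.983, 58/60 = 0.967, 28/30 = 0.933, so about 2%, 3% and 7% too low.

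The range is shown because the SAP does not say which covariates are fixed per woman.

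**Intervals.** Data were simulated for one tissue at four visits (baseline, months 2, 4 and 6). Fixed effects were time, compliance, BMI, cell composition and baseline age, with a random intercept and slope. Each data set was fitted by ML and by REML, and Kenward-Roger (KR) was computed from the REML fit.

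Assumptions not in the SAP: intercept SD 0.35, slope SD 0.25, residual SD 0.25, complete data, compliance and BMI constant within woman, two-sided testing, and a fixed time term (equation 1 carries time only as a random slope). There were 1,500 runs at n = 60 and n = 30, and 800 at n = 120. The Monte Carlo error of a coverage is √(0.95 × 0.05/1500) ≈ 0.6 points, or √(0.95 × 0.05/800) ≈ 0.8 points at n = 120.

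| n | effect | SE, ML/REML | width, ML 1.96 / KR t | coverage, ML 1.96 | coverage, REML 1.96 | coverage, KR t | ML interval excludes 0 but KR p ≥ 0.05 (null data) |
|---|---|---|---|---|---|---|---|
| 120 | time | 0.995 | 0.985 | 94.6% | 94.9% | 95.1% | 0.5% |
| 120 | compliance | 0.982 | 0.964 | 94.6% | 95.0% | 95.4% | 0.7% |
| 60 | time | 0.990 | 0.970 | 94.1% | 94.4% | 95.1% | 0.9% |
| 60 | compliance | 0.965 | 0.927 | 93.6% | 94.4% | 95.1% | 1.5% |
| 30 | time | 0.980 | 0.939 | 93.6% | 93.9% | 94.8% | 1.2% |
| 30 | compliance | 0.928 | 0.852 | 90.5% | 92.5% | 94.9% | 4.5% |

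**Source of the shortfall.** For compliance at n = 60 the gap to KR is 95.1 − 93.6 = 1.5 points. Of this, 94.4 − 93.6 = 0.8 is recovered by REML alone, and 0.7 by the t quantile and the KR covariance. At n = 30 the gap is 94.9 − 90.5 = 4.4 points: 2.0 from REML and 2.4 from the rest. For time, REML alone recovers only 0.3 points at either size.

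**The case against.** The strongest reply is that the SAP never commits to ML Wald intervals. The ML sentence concerns estimation of the coefficients, and the ML point estimates are not in question. Equation 1 as printed would run under REML, and Kenward-Roger applies only if p-values are wanted. A reader might infer that the reported intervals will be too narrow and will conflict with the p-values. The documents do not support that. They leave the interval method open, so undercoverage is a possible consequence and not a stated one. This part of the reply stands.

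It is also fair that treating compliance and BMI as fixed per woman leans towards a larger ML effect. Section 3.4 builds the compliance score from the days between visits, so it can vary by visit, and BMI can change during the intervention. The compliance figures therefore rest on that assumption, whereas the time figures are smaller throughout. The diet sub-study, at 120 women, is practically nominal.

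On equation 2, a reader might infer that neither ML nor Kenward-Roger can be used with glmer. That goes too far: ML is how a generalised linear mixed model is fitted, while REML and Kenward-Roger are what is unavailable. Section 6.4.4 introduces both equations as examples of linear models and names the lmer function, so glmer looks like a slip.

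The reply does not remove the mismatch between the two statements in section 6.4.4, or the downward bias in the reported variances.

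**Conclusion.** The point holds as a minor one. ML estimation with Kenward-Roger p-values is not one coherent fit, the interval method is unspecified, and ML understates the between-woman variances that the section reports.

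Any loss of coverage is conditional on ML intervals with 1.96, on the assumed variance components, and on person-level compliance. On those terms it cannot be told from nominal at 120 women, is small at 60, and is material at 30 for compliance. Only part of it is due to ML.

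A reader might infer that the primary result is at risk. Section 6.4.3 uses paired Wilcoxon tests, which are untouched. Only the optional mixed-model version allowed in section 5.4.1 could be affected, if it were fitted in the same way. The SAP calls the study predominantly exploratory, which also limits the weight of this point.

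**What to change.** Replace the two statements in section 6.4.4 with one rule: linear mixed models are fitted by REML; p-values and 95% confidence intervals both use the Kenward-Roger covariance and degrees of freedom from that fit; ML is used only for likelihood-ratio comparison of fixed-effect structures. Report the variance components from the REML fit. In equation 2 write lmer instead of glmer, because the score is treated as continuous and the stated p-value method is not available for a generalised linear mixed model. Apply the same rule to the linear mixed models for clinical and blood outcomes (6.5.3 and 6.7.2), where no estimation method is given.

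The cost is SAP wording only, with no new data. Intervals become slightly wider than ML intervals with 1.96. For compliance under the assumptions above, the factor is 1/0.964 = 1.04 at 120 women, 1/0.927 = 1.08 at 60 and 1/0.852 = 1.17 at 30.
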